1. SUMMARY

1.1. Identification of the study

Title of study: PRONOCOST study. Cost-effectiveness pharmacoeconomic study of a standardized multidisciplinary weight loss method (PronoKal® Method) to improve health condition of obese patients with associated comorbidities.

Protocol code: PRO-COST-2016-02

1.2. Type of study

Prospective, observational, multicenter study based on a registry of patients with obesity and associated comorbidities undergoing a standardized multidisciplinary weight loss method with a 2-year follow-up.

01.7. Primary objective

To assess the Cost-effectiveness of a standardized weight loss method (Pronokal® Method) treatment to improve the health condition of obese patients with comorbidities and thereby reduce healthcare expenditure (pharmacological treatment, incidence of complications, use of health resources) and work absenteeism.

1.8. Secondary objectives

- Assess short and long-term weight loss and waist circumference reduction
- Assess the degree of clinical and laboratory improvement of cardiovascular risk factors (HTN, diabetes, dyslipidaemia) associated with weight loss
- Evaluate patient quality of life improvement in relation to weight loss
- Assess the tolerability and safety of the weight loss treatment.

1.9. Follow-up and duration of the study

Patients will be monitored for 2 years.

1.10. Schedule

Start of study: April 2017

End of Recruitment Period: June 2018

End of study: June 2020

2. INTRODUCTION

Obesity is a complex medical problem, which has been declared a global epidemic by the World Health Organization. The increase in its prevalence implies significant rises in healthcare system costs, both directly and indirectly, together with a quality of life deterioration.

In Argentina, as in most countries, obesity is a problem that affects more and more people. According to data published by WHO¹, the prevalence of obesity in the country has increased from 23.7% of the adult population in 2010 to 26.5% in 2014.

It is a multifactorial disease that can be associated with multiple comorbidities as it acts as a risk factor for the development of pathologies such as cardiovascular disease, type 2 diabetes (T2DM), various cancers, respiratory problems and arthritis².

Obesity generates a very high socioeconomic and disease burden, which compromises both the health of the population and public and private finances. The importance of treating and preventing obesity lies in reducing the impact of its complications in the quality of life and in its economic costs (including comorbidities and premature deaths attributable to overweight/obesity) that not only affect healthcare expenditure, but are also accompanied by a decrease in labour productivity².

Many studies have highlighted the increased costs associated with overweight and obesity, and how their progressive incidence suggests that in 15 years, in countries such as the United States or the United Kingdom, medical costs associated with the combined treatment of obesity and associated preventable diseases will increase by \$48-66 billion/year and by £1.9-2 billion/year respectively³. Similarly, in a health survey in which data were collected from more than 17,000 people, an association between BMI and the annual rates of outpatient visits and hospitalization days, annual cost of visits, ambulatory pharmacy and laboratory services expenditure, and the total cost of health care (including inpatient and outpatient) was confirmed. Specifically, the total annual mean costs were 25% higher among subjects with a BMI of 30 to 34.9 kg/m² compared to a BMI of 20 to 24.9 kg/m² and 44% higher among those with a BMI of 35 kg/m² or higher. These costs were mainly explained by the presence of coronary disease, hypertension and diabetes⁴. Other studies have also shown the impact of obesity and its complications on productivity. For example, a European study in Sweden found that obese subjects not only had a significantly higher healthcare expenditure on medication, but also that the number of sick leave days was 1.4 to 2.4 times higher and their probability of getting a disability pension multiplied from 1.5 to 2.8 times when compared to normal weight people⁵.

Obesity has biological, physiological, psychological, environmental and economic basis, which operate at several levels, including molecular and genetic mechanisms. Consumption habits of sugars and fats could be due to metabolic imbalances. The glycaemic index of foods, differences between individuals to metabolize glucose and insulin resistance are considered physiological causes of obesity. Psychological causes point to addictive behavioural patterns. Environmental causes emphasize

interpersonal influences and social norms and standards. And for their part, economic factors are related to the living conditions of individuals who suffer from weight problems and food prices. Thus, the increase in weight can be attributed to the consumption of foods high in calories added to increasingly sedentary life patterns.

The standardized multidisciplinary method under study (PronoKal® Method) is a personalized weight loss program under medical supervision. Its purpose is to maintain the body's weight through food re-training and the continued support of a team of dietician-nutritionists.

Based on a protein diet, this method is developed according to the characteristics of the patient and contemplates the participation of a multidisciplinary team that includes medical control, dietary-nutritional monitoring, physical activity and emotional support. Thus, the aim is, on the one hand, to produce rapid weight loss, especially at the expense of fat mass, and on the other hand to achieve a long-term maintenance of the results obtained.

Thus, in addition to a dietary pattern, the method contemplates other factors involved in the pathophysiology of obesity, such as nutritional education, physical activity and emotional support, all of which must be combined under medical supervision to ensure a safe clinical progression of the patient.

In addition to weight loss, other aspects need to be modified in the treatment of the obese patient, so that appropriate behaviours are adopted, resulting in the maintenance of the correct weight.

The basic pillars for the treatment of obesity are changes in lifestyle, including a dietary plan, adjustment of physical activity and emotional support. Thus, the management of obesity requires a multidisciplinary approach that adapts to the characteristics of the patient and allows greater effectiveness in the long term and the optimization of healthcare resources used in the fight against obesity.

Under these premises, the clinical application of the method under study is established through the intervention of a Multidisciplinary Specialist Team:

- 1. Doctor:** clinical assessment, treatment prescription and patient follow-up.
- 2. Physical activity:** guidance and advice to perform adequate physical activity, aimed at increasing caloric expenditure and re-adjusting the energy balance.
- 3. Dietitians:** accompany and advise on nutrition and food choices throughout the treatment.
- 4. Psychological support:** reinforcement of the patient's psychological status contributing to boost the patient's motivation in order to reach his/her short, medium and long-term goals.

The aim of this standardized multidisciplinary method is to decrease the weight of obese patients, which is expected to improve the comorbidities associated with obesity

PRONOCOST study. Cost-effectiveness pharmacoeconomic study of a standardized multidisciplinary weight loss method (PronoKal® Method) to improve health condition of obese patients with associated comorbidities.

The present study is designed to make a Cost-effectiveness assessment of the standardized multidisciplinary weight-loss treatment (PronoKal® Method) in obese patients with associated comorbidities, in order to improve the subjects' health condition, healthcare expenditure and work absenteeism as a consequence of their comorbidities.

3. STUDY OBJECTIVES

3.1. Primary objective

To assess the Cost-effectiveness of a standardized weight loss method (PronoKal® Method) treatment to improve the health condition of obese patients with comorbidities and thereby reduce healthcare expenditure (pharmacological treatment, incidence of complications, use of health resources) and work absenteeism.

3.2. Secondary objectives

- Assess short and long-term weight loss and waist circumference reduction
- Assess the degree of clinical and laboratory improvement of cardiovascular risk factors (HTN, diabetes, dyslipidaemia) associated with weight loss
- Evaluate patient quality of life improvement in relation to weight loss
- Assess the tolerability and safety of the weight loss treatment.

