10.2. Analysis of objectives

The primary objective analysis will include:

- Costs of weight loss treatment estimated from the cost of: protein products and dietary supplements + number of control visits + number of laboratory tests performed
- Healthcare expenditure estimated as the sum of the following costs: pharmacological treatment of associated comorbidities, incidence of

complications (visits to his/her primary care physician, a specialist or emergency department for acute complications, treatment of acute complications, number of hospital admission days, antibiotic treatment), consumption of health resources (visits to the general practitioner, visits to specialists, laboratory tests)

- Work absenteeism, estimate of the number of work leave days + hours of work absenteeism due to health problems or medical visits.

In order to evaluate if the weight loss treatment is improving the health of patients and reducing health expenditure and absenteeism, the healthcare expenses and work absenteeism estimated from the doctor's records corresponding to the 6 months prior to the initiation of the weight loss treatment will be compared with data recorded at follow-up visits over the 2-year follow-up. Likewise, the doses and number of drugs required by patients for the treatment of their comorbidities before the weight loss and at the control visits during weight loss and up to completing the 2 years of follow-up will be compared.

As secondary objectives, the efficacy of the weight loss treatment will be studied by comparing the anthropometric parameters of the initial visit with those of the follow-up visits (weight, body mass index and waist circumference). Likewise, any improvement in laboratory parameters and blood pressure during the follow-up will be studied. Changes in quality of life scores (SF-12) will also be assessed between the initial visit and the end of each treatment stage.

For all objectives, the comparisons between qualitative variables will be made using the Chi square test or the Fisher exact test, and the comparison between quantitative variables will be performed using the Student's t-test (in the case of 2 groups) or by the one-way ANOVA test (for 3 or more groups). If the conditions for the Student's t-test or the Anova test are not met, the non-parametric Mann-Whitney U test (2 groups) or the Kruskal-Wallis test (for 3 or more groups) will be used.

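### The quality-of-life objective, and less firmly the risk-factor objective, asks about a relation to weight loss that no analysis in section 10.2 estimates

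*Combined protocol and SAP*

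**What the plan says.** Section 3.2 (repeated in section 1.8) lists two secondary objectives that mention weight loss alongside another outcome:

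- Quality of life: "Evaluate patient quality of life improvement in relation to weight loss".
- Risk factors: "Assess the degree of clinical and laboratory improvement of cardiovascular risk factors (HTN, diabetes, dyslipidaemia) associated with weight loss".

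Section 10.2 describes three separate secondary analyses:

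- Weight: "comparing the anthropometric parameters of the initial visit with those of the follow-up visits (weight, body mass index and waist circumference" (the stated measure of efficacy).
- Laboratory values and blood pressure: "any improvement in laboratory parameters and blood pressure during the follow-up will be studied".
- SF-12: "Changes in quality of life scores (SF-12) will also be assessed between the initial visit and the end of each treatment stage".

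One list of tests then serves every objective. For categorical data, "the comparisons between qualitative variables will be made using the Chi square test or the Fisher exact test". For continuous data, the plan names the "Student's t-test (in the case of 2 groups) or by the one-way ANOVA test (for 3 or more groups"), and if their conditions fail, "the non-parametric Mann-Whitney U test (2 groups) or the Kruskal-Wallis test (for 3 or more groups) will be used". The groups are not defined anywhere in section 10.

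**The concern.** A question about a relation needs an analysis in which both quantities appear together, patient by patient. Section 10.2 puts weight change in one analysis and SF-12 change in another. Two means that move over the same two years do not show that the patients who lost more weight are the ones whose scores rose.

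The final report could therefore state that weight fell and SF-12 improved, and present that as meeting the objective, although the result would look the same if the two changes were unrelated within patients. The design adds to this. There is no comparator (section 4), and the programme combines diet, physical activity, psychological support and frequent contact (sections 2, 6 and 7.2), so a mean improvement has several possible sources.

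**Working it through.** **Step 1. Objectives against analyses.**

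| Objective (3.2) | Relation asked for | Analysis in 10.2 | Does weight change enter? |
|---|---|---|---|
| Quality of life | Explicit | SF-12, initial visit to end of each stage | No |
| Risk factors | Arguable (see objection) | Improvement in laboratory values and blood pressure during follow-up | No |

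Sections 10.1 and 10.2 contain no correlation, regression, model with weight as covariate, or weight-loss category. The documents give no power or effect figure for these objectives, and the 200 patients of section 5.3 have no derivation, so there is no stated figure to reproduce.

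**Step 2. Why a mean-change result does not carry the relation.** Let each patient's improvement have mean 0.5 SD (assumed), with n = 200. The expected size of a one-sample test of mean change is about 0.5 × √200 = 7.07 standard errors. The correlation between improvement and weight change does not appear in that expression. A simulation (4,000 runs per row, test level 0.05) confirms it:

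| True correlation with weight change | Mean-change test significant | Association test significant |
|---|---|---|
| 0 | 100% | 4.75% |
| 0.3 | 100% | 98.85% |
| 0.6 | 100% | 100% |

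The mean-change result is the same in all three rows. Only the association test tells them apart.

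**Step 3. Is an association analysis feasible?** Inputs: n = 200 from section 5.3; significance level 0.05 from section 10.2, taken as two-sided because the plan does not say; 80% power assumed. Using Fisher's z, the detectable r = tanh[(1.960 + 0.842)/√(n − 3)].

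- n = 200: tanh(2.802/√197) = tanh(0.1996) = 0.197.
- n = 120 (40% not analysable, assumed): tanh(2.802/√117) = tanh(0.2590) = 0.253.
- n = 80 (60% not analysable, assumed): tanh(2.802/√77) = tanh(0.3193) = 0.309.

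These are for a simple correlation at one time point, not for an adjusted mixed model. They show feasibility only.

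**Step 4. Are the data there?** From section 7.2:

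- Follow-up anthropometry and blood pressure are recorded by the dietitians: fortnightly, then monthly, then quarterly or half-yearly.
- SF-12 is recorded by the doctor at the end of each stage.
- Laboratory results at follow-up are recorded by the doctor. HbA1c and LDL-C are itemised only for the pre-inclusion panel, although section 9.2 makes the glycaemic and lipid profiles endpoints.
- Medication changes are recorded by both.

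Weight and SF-12 thus exist for the same patients but not necessarily on the same day. By section 6, stage 1 ends at month 2 and stage 2 at month 2 + 4 = 6 for initial BMI 30 to 35, against months 3 and 3 + 6 = 9 for initial BMI above 35. End-of-stage values therefore fall at different times in the two BMI groups, and time since start has to be in the model.

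**The case against.** The strongest reply has four parts.

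**The listed tests are not tied to visits.** This stands. A reader might infer that none of the named tests could address the relation. The text does not support that: the t-test, ANOVA, Mann-Whitney and Kruskal-Wallis tests compare independent groups, and could compare SF-12 change across weight-loss categories. But the plan defines no such categories. Bands chosen after seeing the data, at 0.05 across many outcomes, would be open to selection.

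**The risk-factor wording is ambiguous.** This also stands. The phrase can mean improvement accompanying the weight-loss programme, and section 10.2 seems to read it so, since it moves from treatment efficacy straight to laboratory values and blood pressure. On that reading, change from baseline answers the objective. The quality-of-life wording is much harder to read this way, so the point rests mainly there.

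**A graded relation would not isolate weight loss.** Correct. A reader might infer that, without a control group, a dose-response with weight would separate a weight-loss effect from time, attention or drug changes. It would not: patients who lose more may also adhere better and attend more, and drug doses change during follow-up and are themselves outcomes (sections 9.1 and 10.2). The analysis is needed because the objective asks for it, not because it settles causation.

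**These are secondary objectives of an observational registry.** True; the primary cost and absenteeism analysis is untouched. That limits the weight of the point but does not remove it.

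**Conclusion.** The point holds for the quality-of-life objective and, less firmly, for the risk-factor objective. As written, section 10.2 answers whether SF-12 changed, not whether the change goes with weight loss.

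It would be too strong to say the study cannot answer these objectives. Weight, blood pressure, laboratory results and SF-12 are collected in the same patients; what is missing is a specified analysis and a rule for matching measurements.

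No bias in a stated figure is claimed. The size of the point is one explicit secondary objective, and arguably a second, without a matching analysis. With 200 patients a correlation of about 0.20 is detectable; with 120 or 80, about 0.25 or 0.31. This rests on two-sided 0.05, 80% power and assumed numbers analysable. For diabetes or dyslipidaemia outcomes the relevant number may be well below 200, since section 5.1 asks for only one of four comorbidities and the documents do not give the split. The change should be made, but it is not critical to the primary objective.

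**What to change.** Add to section 10.2:

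1. **SF-12.** A pre-specified regression or mixed model of change in the physical and mental scores on percent weight change from baseline, adjusted for baseline score, age, sex and months since start. Use the weight recorded nearest to each end-of-stage SF-12, within a stated window.
2. **Weight-loss bands.** Tabulate SF-12 change by bands fixed before the data are examined (for example below 5%, 5 to 10%, above 10%).
3. **Glycaemic, lipid and blood pressure outcomes.** Run the same analysis where follow-up values exist, and account for recorded medication changes, for example by adjustment or by a sensitivity analysis in patients whose drugs did not change. State which laboratory values are repeated at follow-up.
4. **Interpretation.** Report the results as associations that do not separate weight loss from adherence, attention or time.

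The alternative is to reword the two objectives in sections 1.8 and 3.2 as change over time, which section 10.2 already addresses.

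The cost is some added text in the plan, a few extra tables and a matching-window rule. No new type of data is needed for SF-12. For laboratory outcomes the analysis depends on the tests actually being repeated.

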4. STUDY DESIGN

Prospective, observational, multicenter study based on a registry of patients with obesity and associated comorbidities undergoing a standardized multidisciplinary weight loss method with a 2-year follow-up.

No randomization or administration of drug treatment is intended as a consequence of the patient's participation in the study.

5. STUDY POPULATION

Obese patients with obesity-associated comorbidities treated with the standardized multidisciplinary weight loss method (PronoKal® Method).

5.1. Inclusion criteria

- Patients of both sexes 18 years of age or older
- Patients with overweight or obesity ($BMI > 30 \text{ kg/m}^2$) with at least one or more of the following comorbidities associated with obesity:

- Type 2 diabetes mellitus
- Arterial hypertension
- Dyslipidemia
- Hyperuricemia

Those who are under pharmacological treatment with two or more drugs (oral antidiabetic and/or lipid-lowering agents and/or antihypertensive and/or hypouricemic agents)

- Patients who agree to attend the follow-up visits at the Pronokal centre, in Buenos Aires.
- Patients who agree to participate and provide a signed informed consent

5.2. Exclusion criteria

- Patients who do not sign the informed consent
- Pregnant or breastfeeding patients.
- Patients with severe eating disorders, alcoholism, or substance abuse.
- Patients with severe psychological disorders (e.g., schizophrenia, bipolar disorder).
- Patients with liver failure.
- Patients with kidney failure.
- Patients with type 1 DM or insulin-dependent, or currently under insulin treatment, or candidates for insulin treatment in a short period of time.
- Patients with obesity caused by other endocrine diseases (except type 2 DM).
- Patients with blood disorders.
- Patients with cancer.
- Patients with cardiovascular or cerebrovascular disease (heart rhythm disorders, recent infarction [<6m], unstable angina, decompensated heart failure, recent stroke [<6m]).
- Patients with renal lithiasis.
- Patients with cholelithiasis.

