7.2. Follow-up period

The expected follow-up period for each patient will be 2 years from the time of inclusion, recording data during the weight loss and maintenance periods. The registry of patient data for this study will be made by the doctor and the dietitians/nutritionists who will regularly see the patient in the face-to-face visits at the Pronokal centre. For this, a specific form will be designed in which information about the variables to be studied will be collected.

Before starting treatment with the standardized multidisciplinary method and its inclusion in the study, the physician will have performed a first patient pre-inclusion visit (day -15) to request complementary tests (laboratory and ECG) and rule out the existence of contraindications to the ketogenic diet part of the weight loss program.

The study will begin with the baseline visit (day 0) in which the inclusion and exclusion criteria will be confirmed, the signing of informed consent will be obtained and the multidisciplinary treatment will be prescribed, followed by 6 control visits: 2 visits during the ketogenic stage (1-month after the start and at the end of ketosis), 2 visits during the physiological adaptation phase (at 4 or 5 months and at the end of stage 2) and 2 follow-up visits during the maintenance up to the 2-year completion. Regardless of the visits established in this protocol, the doctor will make as many visits as he/she deems necessary for good patient control.

On the other hand, dietitians/nutritionists, according to the methodology of the program, will carry out a face-to-face follow-up of the patient, which will be fortnightly during the ketogenic diet, monthly during the physiological adaptation of stage 2 and quarterly or semi-annual during the maintenance stage.

In the **pre-inclusion visit (day -15)**, the physician will perform a first clinical assessment of the patient. He/she will record the sociodemographic data, history of diabetes, comorbidities, pharmacological treatments. He/she will request complete laboratory tests and will perform an electrocardiogram to rule out contraindications and verify the inclusion/exclusion criteria. The said laboratory tests will include:

- Complete blood count and leukocyte formula
- Hydrocarbon metabolism: fasting glycemia, HbA1c, insulinemia
- Lipid profile: total cholesterol, LDL-C, HDL-C, triglycerides
- Transaminases: GOT, GPT, gammaGT

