- Renal profile: creatinine, glomerular filtration, creatinine clearance, microalbuminuria
- Nitrogen balance: urea, uric acid
- Thyroid profile: TSH, T3, T4
- Ionogram: Na, K, Cl, Ca, Mg

In the **initial visit (day 0)**: In this visit, a physical examination will be performed and data related to weight (weight, BMI, waist circumference), as well as data on comorbidities associated with obesity (type of pathology, pharmacological treatment, complications in the last year) will be recorded. After checking the inclusion/exclusion criteria, the patient information sheet will be given and the informed consent will be obtained. During this visit, the patient's quality of life will be assessed (with the SF-12 quality of life questionnaire) and treatment will be prescribed according to the method (PronoKal® Method), which will begin with phase 1 of the active stage.

PRONOCOST study. Cost-effectiveness pharmacoeconomic study of a standardized multidisciplinary weight loss method (PronoKal® Method) to improve health condition of obese patients with associated comorbidities.

In the **follow-up visits - Recorded by the doctor**. In the regular check-ups throughout the course of treatment, the physician will record: any discomfort or side effect related to weight loss treatment and whether there has been any change in the comorbidities associated with obesity (laboratory results, medication, complications, etc.). At the end of each stage the doctor will assess the patient's quality of life through a questionnaire.

In the **follow-up visits - Recorded by dietitians/nutritionists**. During the interviews that the dietitians/nutritionists will have with the patients, and parallel to the doctor's records, the following details will be recorded:

- Clinical data: anthropometric data and blood pressure
- Medication changes
- Onset of complications (e.g., hypertensive crisis, ...)
- Hospital admissions
- Work absenteeism: number of days and cause....

In case of early withdrawal from the study, the doctor will write the dropout date and the reason, in study completion form.

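### Entry rules set infarction and stroke to zero in the 6-month pre-treatment window, while their costs can count in follow-up, so this part of the before/after cost comparison can only stay level or rise

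*Combined protocol and SAP*

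**What the plan says.** Section 5.2 excludes "Patients with cardiovascular or cerebrovascular disease (heart rhythm disorders, recent infarction [<6m], unstable angina, decompensated heart failure, recent stroke [<6m"]). Within that list only infarction and stroke carry a time window. Other exclusions are stated as a condition the patient has at entry, for example "Patients with cancer" and "Patients with type 1 DM or insulin-dependent, or currently under insulin treatment, or candidates for insulin treatment in a short period of time".

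Section 7.2 fixes when eligibility is settled: "The study will begin with the baseline visit (day 0) in which the inclusion and exclusion criteria will be confirmed". Treatment is prescribed at that same visit. Follow-up is then set as "The expected follow-up period for each patient will be 2 years from the time of inclusion".

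Section 10.2 defines the primary contrast: expenditure and absenteeism "corresponding to the 6 months prior to the initiation of the weight loss treatment will be compared with data recorded at follow-up visits" over the 2 years. The summed expenditure covers comorbidity drugs, routine visits, laboratory tests and a complications item that includes "treatment of acute complications, number of hospital admission days, antibiotic treatment". No cause of admission is left out. Section 7.2 has the dietitians record "Onset of complications (e.g., hypertensive crisis" and similar events, and hospital admissions, again without limit by cause.

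**The concern.** The primary objective (section 3.1) names a reduction in the incidence of complications as one route to lower expenditure. Section 4 describes a single cohort without randomization and no comparison group is described, so the before/after contrast carries the claim.

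If the entry rules remove certain acute events from the pre-treatment window but leave them free to occur afterwards, that part of the contrast is asymmetric by construction. A real saving elsewhere could be partly masked, or a rise in acute-event cost could be read as harm from the programme when it reflects selection at entry. Neither a common time unit nor a paired test removes this, because the zero comes from who may enrol and not from how the data are scaled or tested.

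**Working it through.** **Do the two windows coincide?** The 5.2 look-back for infarction and stroke is under 6 months, and eligibility is confirmed on day 0 (7.2). The 10.2 cost window is the 6 months before treatment starts, and treatment is prescribed on day 0. Apart from any few days between prescription and start, these are the same months. No eligible patient can bring an acute infarction or stroke into the pre-treatment window.

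**Are the events open in follow-up?** Yes. 10.2 costs acute complications and admission days without restriction by cause, and 7.2 records admissions. The documents do not provide for removing or censoring a patient who develops an excluded condition, and they give no adjustment or sensitivity analysis.

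**Is the total zero at baseline?** No. Section 5.1 requires treatment with two or more drugs, so drug cost is above zero by rule. Routine visits, laboratory tests and absenteeism are not forced to zero either.

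**Plan's own figure.** The only size figure is 200 patients (5.3). It comes without effect size, standard deviation, event rate, power or dropout, so it cannot be reproduced. The point does not depend on it.

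**Illustration.** The annual rate of infarction and stroke together, r, is assumed, constant and unaffected by treatment; the documents give none.

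- Person-years before: 200 × 0.5 = 100. After, with complete follow-up: 200 × 2 = 400.
- Events expected in an unrestricted pre-treatment window: 100 × r. Under the entry rule: 0.
- Events expected in follow-up: 400 × r; per 6 months, divide by 4.
- Chance of no event before treatment even without the rule (Poisson): exp(−100r).

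| Assumed r per year | Before, unrestricted | Before, under 5.2 | Follow-up total | Follow-up per 6 months | Chance of zero before without the rule |
|---|---|---|---|---|---|
| 0.5% | 0.5 | 0 | 2 | 0.5 | 61% |
| 1% | 1 | 0 | 4 | 1 | 37% |
| 2% | 2 | 0 | 8 | 2 | 14% |

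If 30% dropped out, on average half-way, follow-up would be 400 × (1 − 0.15) = 340 person-years and the totals 1.7, 3.4 and 6.8. The rate per person-year is unchanged.

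**Effect on mean cost.** Let K be the cost of one event as a multiple of a patient's other 6-month cost (also assumed). The spurious rise in mean 6-month cost is r × 0.5 × K.

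- r = 1%: K = 5 gives 0.01 × 0.5 × 5 = 2.5%; K = 20 gives 10%; K = 50 gives 25%.
- Lowest corner: 0.005 × 0.5 × 5 = 1.25%. Highest corner: 0.02 × 0.5 × 50 = 50%.

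**The case against.** The strongest reply is that this concerns one sub-component of a sum dominated by items that do have a baseline, and that the numbers are small. Both parts largely stand. At the assumed rates an unrestricted window would hold only 0.5 to 2 such events, and zero would arise by chance 14% to 61% of the time. The upper cost figures multiply the high ends of two assumptions. Setting 0 events against 2–8 would also be unfair, since it compares 100 person-years with 400; the like-for-like contrast is 0 against 0.5–2 per 6 months.

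A reader might infer that every condition in 5.2 is barred from the pre-treatment 6 months. The text does not support that. Only infarction and stroke have a look-back. A passed stone, or a rhythm disorder or heart-failure episode that resolved in those months, is not clearly excluded. For conditions that persist once present, exclusion by status probably lowers baseline cost, but a zero is not shown. Nor is it established that all such conditions would be costed in follow-up: the one complication named in 7.2 is a hypertensive crisis, which can occur in both periods.

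It can also be said that the baseline visit records complications over the last year, so months −12 to −6 may include infarction or stroke. That is true, but 10.2 draws its comparison from the last 6 months only, so it does not repair the contrast.

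Finally, stripping excluded conditions out of the headline could hide harm from the programme, because screening in 7.2 is meant to rule out contraindications to the ketogenic diet. This is a sound objection to that remedy, and the change proposed here keeps every cost in the headline.

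**Conclusion.** The point holds for infarction and stroke within the acute-complication and admission component. Their pre-treatment value is zero by rule and their contribution can only stay level or rise. This follows from sections 5.2, 7.2 and 10.2 read together and needs no assumption beyond the entry rule being applied as written.

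It does not follow that the primary comparison as a whole starts from zero, or that total expenditure is biased upward on balance. This asymmetry makes follow-up look dearer, so by itself it cannot create a false saving. The two-drug entry rule in 5.1 may push drug cost the other way through regression to the mean. The net direction for total cost cannot be determined from the documents.

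The size is likewise unknown. The illustrated 1.25% to 50% rise in mean 6-month cost rests entirely on assumed rates (0.5–2% per year) and assumed cost multiples (5–50). At the low end it hardly matters; at the high end it could mask a real saving. Since opposing selection effects may meet in one sum, the components need to be seen separately. The plan should be changed on this point, but the flaw does not invalidate the study.

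**What to change.** In section 10.2:

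- Keep all costs in the headline expenditure total.
- Show the acute-complication and admission component separately from drug and routine-care costs, on a common time unit such as cost per patient per 6 months.
- Report infarction and stroke in follow-up, and new onset of the other conditions listed in 5.2, as events and cost per person-year, with no before/after test.
- Add a sensitivity comparison that leaves out infarction and stroke costs, labelled as addressing selection at entry.
- State that a rise in the acute-event component cannot be attributed to the programme from the before/after comparison.

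The cost is a cause code on complications and admissions that are already recorded, plus one extra analysis. No eligibility rule or aspect of patient care changes.
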